### Protocol Change Status

Revision	Date of Revision	Reason for Amendment
A	27 July, 2017	

## Study Outline

- Study Title:** Exoskeleton Treatment of Deconditioning Due to Limited Ambulation Caused by Illness or Injury
- Sponsor:** Ekso Bionics, Inc.  
[name]  
[name]
- Study Description:** A safety and feasibility study of robotic exoskeleton training in deconditioned patients residing in a healthcare facility.
- Overall goal:** We aim to demonstrate that EksoGT™ robotic exoskeleton training can be performed safely with patients who have been hospitalized and are at risk of experiencing a further decline in their physical condition.
- Rationale:** Patients who are hospitalized for several weeks or months are at a higher risk of decline in physical condition and are also at a higher risk of rehospitalization within 30 days of discharge. A program incorporating robotic exoskeleton training may provide sufficient physical support and challenge for patients to maintain a higher level of physical condition than if they did not undergo exoskeleton training.
- Hypothesis:** Robotic exoskeleton training during hospitalization is safe and feasible.
- Design:** Single-arm safety and feasibility study.
- Participants:** Patients who fulfill the inclusion/exclusion criteria.

### Inclusion criteria:

1. A diagnosis of “deconditioned”, defined as the loss of muscle tone and endurance due to chronic disease, immobility, or loss of function.
2. Adults 18 years and older (or as specified by state law).
3. Admitted into a hospital, long-term care facility, skilled nursing facility, or similar.
4. Sufficient upper extremity strength to use a front wheeled walker by manual muscle testing (minimum triceps strength bilaterally of 3/5, shoulder abduction and flexion/extension 4/5).
5. Screened and cleared by a physician for full weight-bearing exercise training.
6. Weigh 220 pounds (100kg) or less.
7. Between approximately 5’0” and 6’4” tall.
8. Standing hip width of approximately 18” or less.
9. Have near normal range of motion in hips, knees and ankles.

### Exclusion criteria:

1. Currently involved in another intervention study.
2. Transferred to the intensive care unit or isolation-room stay.
3. Currently on a ventilator or extracorporeal membrane oxygenation

(ECMO) machine.

4. Currently have a ventricular assist device (VAD) or an automatic implantable cardioverter-defibrillator (AICD).
5. Advanced heart failure - ejection fraction of < 20%.
6. Documented cardiovascular risk from exercise.
7. Resting heart rate <50 bpm or >120 bpm.
8. Uncontrolled or new (within 24 hours) arrhythmias.
9. Resting blood pressure below 90/70 or above 160/100.
10. Oxygen saturation (O2 sat) < 90% during rest.
11. Uncontrolled or severe orthostatic hypotension that limits standing tolerance.
12. Cardiac ischemia within 24 hours.
13. Unresolved or new (within 24 hours) deep vein thrombosis.
14. Concurrent severe neurological pathology/disease or stroke within 72 hours.
15. Open skin ulcerations on any body surfaces in contact with exoskeleton.
16. Acute fracture
17. Osteoporosis
18. Active heterotrophic ossification (HO) of the lower extremity, hip dysplasia, or hip/knee axis abnormalities.
19. Current chemotherapy
20. Inability to speak or understand the English language.
21. Inability to cooperate in tests/exercises.
22. Hip flexion contracture greater than ~17°.
23. Knee flexion contracture greater than 12°.
24. Unable to achieve neutral ankle dorsiflexion with passive stretch (neutral with max 12° knee flexion).
25. Cognitive impairments - unable to follow 2 step commands or to communicate pain or to stop session.
26. Pregnancy
27. Any reason the physician may deem as harmful to the participant to enroll or continue in the study.

- Sample Size:** Forty (40) Participants who meet the inclusion and exclusion criteria will be enrolled.
- Blinding:** Blinding will not be implemented during this study.
- Setting/Sites:** Hospital, long-term care facilities, or skilled nursing facilities (up to 5 clinical sites). Sites are to be chosen based on having Ekso Level 2 training certification, location, enrollment capabilities, and resources.
- Duration:** Each enrolled Participant is expected to engage in this study for up to 2 weeks. The duration of the study is expected to be approximately 6 months.
- Assessment periods:** The study consists of a screening period and up to 5 training sessions with assessments for safety.
- Primary Objective:** To demonstrate that a multi-day robotic gait training regimen is safe and feasible for deconditioned patients who have been admitted to a healthcare facility.

**Primary End Point:** The primary endpoint is safety defined as the number of device-related serious adverse events per Participant and overall during the study period.

### **List of Abbreviations**

- AE – adverse events
- BMI – body mass index
- BP – blood pressure
- BWS – body weight support
- CRF – case report form
- DSMB – Data Safety Monitoring Board
- FDA – Food and Drug Administration
- GCP – Good Clinical Practice
- IRB – Institutional Review Board
- LE – lower extremity
- PT – physical therapist
- ROM – range of motion
- SAE – serious adverse event
- UE – upper extremity

## **1. Literature Summary and Study Rationale**

Multiple factors can lead to a general decline in the physical condition of adults at any age. Medical challenges posed by illness or injury often result in sedentary behavior followed by a general loss of muscle mass, decreased balance, and increased risk of falling. The Center for Disease Control and Prevention (CDC) states, “As an older adult, regular physical activity is one of the most important things you can do for your health. It can prevent many of the health problems that seem to come with age.” Despite our best efforts, illness and injuries occur and often lead to sedentary behavior and a general deconditioning of adults of all ages. Deconditioning is defined as “the loss of muscle tone and endurance due to chronic disease, immobility, or loss of function.” Falvey et al studied one group of adults that experienced “hospital-associated deconditioning” or HAD, defined as “marked deficits in physical function secondary to an acute hospitalization” and stated that “68% of patients are discharged from post-acute care settings below their prehospitalization level of function.” Further, hospitalized older adults are 61 times more likely to develop disability in activities of daily living (ADLs) than those who are not hospitalized. In fact, older adults who are discharged with poor physical function have 3 times the odds of being rehospitalized within 30 days than older adults with medically complex conditions and high physical function. This decline in function during acute hospitalization is considered to be partially avoidable.

Injury and illness leading to confinement and general inactivity does not occur solely in acutely hospitalized patients. Long-term care facilities and skilled nursing facilities admit adults with a variety of conditions that limit daily ambulation. This pilot study aims to enroll a small group of adults that have experienced a loss of physical strength due to limited ambulation during convalescence and to offer a short exercise program using a robotic exoskeleton that provides support and physical challenge during ambulation.

## **2. Study Objectives**

The primary objective is to demonstrate that a multi-day robotic rehabilitation regimen is safe and feasible in deconditioned patients who have been admitted to a facility.

## **3. Study Design**

This is a single-arm, short term, safety and feasibility study.

## **4. Study Endpoints**

The primary endpoint is safety defined as the number of device-related serious adverse events per Participant and overall during the study period.

## **5. Participant Enrollment**

Participants are inpatients that are identified and recruited from participating facilities. Eligible patients will be presented with a study consent form. The point of enrollment is after the patient has met the inclusion/exclusion criteria, and has signed the study consent form.

## **6. Duration of Participation/Study**

Each Participant will be enrolled for up to 2 weeks or until the Participant elects to terminate participation, is discharged from the facility, or a physician removes the Participant from the study.

## 7. Inclusion/Exclusion Criteria

### Inclusion criteria:

1. A diagnosis of “deconditioned”, defined as the loss of muscle tone and endurance due to chronic disease, immobility, or loss of function.
2. Adults 18 years and older (or as specified by state law).
3. Admitted into hospital, long term care facility, skilled nursing facility, or similar.
4. Sufficient upper extremity strength to use a front wheeled walker by manual muscle testing (minimum triceps strength bilaterally of 3/5, shoulder abduction and flexion/extension 4/5).
5. Screened and cleared by a physician for full weight-bearing exercise training.
6. Weigh 220 pounds (100kg) or less.
7. Between approximately 5’0” and 6’4” tall.
8. Standing hip width of approximately 18” or less.
9. Have near normal range of motion in hips, knees, and ankles.

### Exclusion criteria:

1. Currently involved in another intervention study.
2. Transferred to the intensive care unit or isolation-room stay.
3. Currently on a ventilator or extracorporeal membrane oxygenation (ECMO) machine.
4. Currently have a ventricular assist device (VAD) or an automatic implantable cardioverter-defibrillator (AICD).
5. Advanced heart failure - ejection fraction of < 20%.
6. Documented cardiovascular risk from exercise.
7. Resting heart rate <50 bpm or >120 bpm.
8. Uncontrolled or new (within 24 hours) arrhythmias.
9. Resting blood pressure below 90/70 or above 160/100.
10. Oxygen saturation (O2 sat) < 90% during rest.
11. Uncontrolled or severe orthostatic hypotension that limits standing tolerance.
12. Cardiac ischemia within 24 hours.
13. Unresolved or new (within 24 hours) deep vein thrombosis.
14. Concurrent severe neurological pathology/disease or stroke within 72 hours.
15. Open skin ulcerations on any body surfaces in contact with exoskeleton.
16. Acute fracture
17. Osteoporosis
18. Active heterotrophic ossification (HO) of the lower extremity, hip dysplasia, or hip/knee axis abnormalities.
19. Current chemotherapy
20. Inability to speak or understand the English language.
21. Inability to cooperate in tests/exercises.
22. Hip flexion contracture greater than ~17°.
23. Knee flexion contracture greater than 12°.
24. Unable to achieve neutral ankle dorsiflexion with passive stretch (neutral with max 12° knee flexion).
25. Cognitive impairments - unable to follow 2 step commands or to communicate pain or to stop session.
26. Pregnancy
27. Any reason the physician may deem as harmful to the participant to enroll or continue in the study.

## **8. Screening, Enrollment, and Treatment**

**Screening and Informed Consent.** Study Participants will be recruited after the Institutional Review Board (IRB) has approved the study. The investigator or the investigator's designee will inform all patients who express willingness to enter the study about the purpose of the study, the required testing, procedures, and assessments, the expected duration, and the potential risks and benefits of study participation.

Potential Participants are identified by the investigator or the investigator's designee. The investigator or designee will review the patient's history to determine the patient's initial eligibility for study entry. After determining an applicant's initial eligibility status, the applicant may be offered the opportunity to participate in the study and will be given the opportunity to further discuss the available treatments, the risks and benefits, alternative therapies, and study requirements with the investigator or investigator's designee during the consent process. The applicant will be informed by the investigator or investigator's designee that he/she is free to change his/her mind and may withdraw from the study at any time without prejudicing further care. The study investigator or designee will give the applicant an informed consent document to read and time to ask questions and think about his/her decision prior to signing and dating the consent form. Further, the investigator or the investigator's designee will inform the applicant that as a Participant in a study, his/her medical records may be reviewed by the Sponsor and representatives of regulatory bodies, and that study information will be used during the analysis of the results of the clinical study, but that the identity of the Participant would not be disclosed to any reports emanating from this study. Applicants must sign a consent form before any study-specific evaluations or procedures are performed.

**Applicants become enrolled as Participants in the study upon signing the consent form.** The original signed consent form will be returned to the investigator and filed in the Participant's study file. The Participant will be given a copy of the signed consent to keep.

Treatment will consist of exercise using the EksoGT described below. Dosage (daily or weekly) and progression of settings (challenge) will be highly individualized due to the heterogeneous population to be enrolled in this study. No participant is expected to exceed 5 sessions in the exoskeleton.

## **9. Ekso Device Description and Safety Features**

The EksoGT is a powered motorized orthosis intended to enable individuals who are experiencing muscular or neurological conditions affecting their lower extremities to perform ambulatory functions such as gait training. (See Figures 1 and 2.) It consists of a fitted metal brace that supports the legs, feet, and torso. It is adjustable to accommodate different length segments and different hip widths. Typically, a physical therapist straps the patient's feet, legs, and torso into the device. When patients become more familiar with the Ekso they may strap themselves in. The straps are designed for the patient to easily get in and out of the device either on their own or with minimal assistance. Soft goods (pads, spacers, straps, and supports) are available for bracing and adapting to various body types. The straps and soft goods are specifically designed to prevent pressure points or other skin issues. There is also a link (Don-DoFF Link) just below each hip joint, which permits abducting the legs while seated to facilitate donning and doffing the device.

Figure 1: The EksoGT in use during gait training of an SCI patient.

[figure not shown]

Figure 2: The EksoGT structure and general dimensions.

The EksoGT manipulates the patient’s legs and waist to stand up, walk over level ground, and then to sit down. Battery powered motors drive knee and hip joints. The batteries are designed to last for approximately three hours of normal use. The patient is required to assist with balance and body positioning using a cane, crutches, or walker, which are provided with the device. The physical therapist operates the device and monitors the patient to ensure balance is maintained. The device is operated in various modes. In some modes, steps are triggered with the attached user interface. In other modes, steps are triggered when the machine is in certain target postures. In other modes, the therapist may adjust the level of assistance provided so that, if the patient has some residual strength, the patient performs some of the walking motion with their own muscles.

The EksoGT has a number of features to ensure patient safety. It is equipped with mechanical hard stops at the limits of healthy Participant ranges of motion to prevent powering the joint of the user to a position that the joint cannot reach. The actuated range of motion at the hip is  $-20^{\circ}$  to  $135^{\circ}$  and the actuated range for the knee is  $0^{\circ}$  to  $120^{\circ}$ . Not all of this range of motion is needed in normal walking; however the ranges of these joints were selected to provide for other necessary functions such as standing and sitting. At the ankle the device is passive, with springs to resist sagittal plane motion, and locked in the other degrees of freedom. The range of motion provided at the ankle is from  $-10^{\circ}$  to  $20^{\circ}$  dorsiflexion with hard stops at the limits of this range to protect the user and a setting to specify the neutral angle.

Redundant position sensing on all of the actuated joints ensures that the motors are always controlled using reliable sensor information. In addition, the device has numerous sensor, motor, and software monitoring systems. If any abnormality is detected (i.e. excess joint speed or force, or if redundant sensors do not agree) the device enters a safe mode, which prevents continued walking and enables the physical therapist to safely remove the patient. The device is also equipped with fail-safe brakes on the actuated knee joints, such that if the device loses power or is shut down for any reason the knees will continue to support the patient. Finally, an emergency disable button is available to instantly shut down the device for any reason. This is implemented via hardware, so it is effective even during a software malfunction.

The EksoGT is intended to be used under the supervision of a physical therapist who has successfully completed the level 2 Ekso Bionics training program. This program covers all aspects of device operation and adjustment, including proctored and individual hands-on experience with

patients. The program also covers methods of ensuring patient safety and requires Participants to demonstrate their knowledge.

Participants must meet all criteria related to the EksoGT per EksoGT Operating Manual. All Ekso training will be conducted using the EksoGT with SmartAssist™ software. The Ekso will be programmed to allow bilateral assist mode with adaptive and fixed swing assist options, as well as unilateral and 2Free modes with neutral, high/low assistance, and high/low resistance options. All pre-gait features will be available during this study.

There is no comparator device in this single -arm study.

Inventory control is not applicable in this trial since sites will use their commercially acquired devices for this study of a new indication for use.

## **10. General Rules for Training Sessions**

1. The goal is to have Participants train in the EksoGT daily for 30-45 minutes per session, or as tolerated, ideally over the entire time of admission, but for no greater than 5 sessions.
2. It is recommended to schedule Ekso during a 45-60 minute session.
3. Patients should achieve at least 5 minutes of stable blood pressure during standing in the EksoGT prior to walking in the device.
4. Participants may use the PreGait function to perform activities in the EksoGT and walk in EksoGT both inside and outside of the trajectory, at the therapist's discretion.

To challenge Participant:

1. In Fixed Assist, lower the swing assist for each leg as appropriate.
2. In Fixed Assist, stance support may be changed from "Full" to "Flex" as appropriate.
3. In FreeGait, stance support should begin at an appropriate level. As Participant improves stance control, support may be reduced as tolerated and clinically appropriate.
4. In FreeGait, swing assist should be assessed at "neutral". If a leg is not able to complete a step, "high"/"low assistance" may be provided for more normalized stepping. If a leg is stepping far outside of the general trajectory, "high"/"low resistance" may be provided for more normalized stepping. Progress to a more symmetrical gait.
5. In FreeGait, set swing support at lower assistance or higher resistance for an appropriate clinical challenge.

## **11. Participant Assessments**

In-person limited screening procedures are conducted to assess minimal trial inclusion. Prior to initiating physical or psychological screening evaluations, study personnel must obtain a signed informed consent. Participant screening can then proceed to ensure the individual meets inclusion/exclusion criteria.

The following information will be obtained during *screening*:

1. Demographic data including date of birth, gender, date of illness (self-reported).
2. Past and current medical history (from medical records).
3. Reason for admission to the facility (from medical records).
4. List of current medications (from medical records).
5. Weight and height (from medical records).
6. Vital signs (HR, BP, O2 sat from medical records).

7. Written documentation from the patient's physician verifying the patient is medically stable and cleared for full weight bearing locomotor training and does not have any conditions that would exclude the Participant (see Inclusion/Exclusion criteria).
8. Current practice of standing or walking, level of assistance required, assistive devices and braces used, and any associated adverse events (self-reported).
9. Range of motion for hip flexion/extension, knee flexion/extension/ ankle dorsi/plantar flexion.
10. Upper extremity MMT to include: shoulder flexion/extension/abduction and elbow extension.
11. Skin check of back, sacrum, shins, and feet (must be done at each visit).

The following data will be collected *per session*:

1. Any adverse events/complications noted following prior to training session and during present session.
2. Assessment of skin integrity of the anterior and posterior torso, anterior tibia, sacral area and bilateral feet (before and after training).
3. Vital signs (HR, BP, O2 sat collected daily).
4. Walk time.
5. Stand/Uptime.
6. Estimated seated rest time.
7. Estimated regular overground walking time (outside of EksoGT).
8. Number of steps total and in each mode of EksoGT.
9. Time spent in each EksoGT mode.

## **12. Adverse Events**

An adverse event (AE) is any untoward medical event that occurs to a study Participant once the individual has signed the informed consent form until the study Participant's last study visit.

Examples include:

- Any sign, symptom, or physical examination finding that worsens in nature, severity or frequency compared to baseline.

A serious adverse event (SAE) is one that meets any of the following criteria:

- Results in death.
- Is life threatening.
- Requires inpatient hospitalization or prolongation of an existing hospitalization.
- Results in persistent or significant disability/incapacity.
- An important medical event that may not result in death, be life-threatening, or require hospitalization, may be considered a serious adverse event when, based upon appropriate medical judgment, it jeopardizes the Participant and may require medical or surgical intervention to prevent one of the outcomes listed in this definition.

A life-threatening adverse event is defined as any adverse experience that places the Participant, in the view of the Investigator, at immediate risk of death from the event as it occurred, i.e. it does not include an event that, had it occurred in a more severe form, might have caused death. ALL serious adverse events must be reported to the Sponsor within 24 hours of the knowledge of the event and reported to the respective IRB as soon as possible, but no later than ten working days after the investigator learns of the event or as required by the IRB. In the event of Participant death, a copy of

death records, medical records pertaining to the events leading up to the death and an autopsy report (if performed) must be sent to the Sponsor as soon as possible. All Participant identifiers other than the Participant number and initials must be removed from the documents submitted to the Sponsor.

A pre-existing condition is one that is present prior to or at the start of the study and is to be reported as part of the Participant's medical history. It should be reported as an adverse event only if the frequency, intensity, or the character of the condition worsens during study participation.

An unanticipated adverse event is one not identified in nature, severity, or frequency in the current protocol.

Adverse events (AE) data collection must begin once the Participant has signed the informed consent document. AEs will continue to be collected each visit during the entire 12-week training period and end at the 6-month visit. In general, AEs should be reported and classified by the investigator using a diagnosis. The diagnosis should be confirmed through specific signs, symptoms, and (if necessary) laboratory tests. Data to be collected will include the description of the event, onset and resolution dates (or whether the event is ongoing), severity, management/treatment, outcome, and determination of the relationship to the device used during training. The relationship of the event to the device used will be further described as related or unrelated to a specific device. If related to a device, the categories will be further described as definitely, probably, or possibly-related using the following definitions:

1. *Definitely device-related*: Any event that is associated with the device by timing and physiology, and was caused or contributed to by the device.
2. *Probably device-related*: Any event that is associated with the device by timing and physiology, and there is a good chance that it may have been caused or contributed to by the device.
3. *Possibly device-related*: Any event that is associated with the device by timing and physiology, and there is a possibility that it may have been caused or contributed to by the device.

Severity of the AE will be coded as to the degree of severity as follows:

- A. *Mild*: Awareness of the event, but easily tolerated.
- B. *Moderate*: Discomfort enough to cause interference with usual activity.
- C. *Severe*: Inability to carry out usual activity. (Not necessarily the same as a Serious Adverse Event. Participants may have a severe flu but not require hospitalization.)

Treatment for the AE includes all of the commercially approved products or standard procedures that are to be administered according to standard medical practice. Investigational products or procedures are not to be used as a treatment for an adverse event. All unresolved AEs should be followed by the investigator until all events are resolved, the event is identified as being a chronic condition, or the Participant is lost to follow-up.

The case report form package for this study includes dedicated adverse event and serious adverse event forms. An independent Data Safety Monitoring Board (DSMB) will assess and adjudicate all SAEs and protocol violations.

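### The objective is safety of the training regimen, but the primary endpoint and the only listed causality item concern the device alone, so a session-caused SAE can be coded unrelated and leave the primary count

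*Protocol*

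**What the plan says.** The claim is about training. The Study Outline's overall goal is to show that "robotic exoskeleton training can be performed safely with patients who have been hospitalized", and its primary objective is "To demonstrate that a multi-day robotic gait training regimen is safe and feasible for deconditioned patients". Section 2 repeats the objective for the regimen.

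The endpoint is about the device. Section 4 and the Study Outline define it as "the number of device-related serious adverse events per Participant and overall during the study period".

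The causality item is also about the device. Section 12 lists the relationship to the device among the adverse event data and adds: "The relationship of the event to the device used will be further described as related or unrelated to a specific device". Related events are graded definitely, probably or possibly. Each grade requires a link to the device in time and physiology, and the lowest also asks only for a possibility that the device caused or contributed to the event.

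On what the regimen consists of, Section 8 says: "Treatment will consist of exercise using the EksoGT described below". Section 9 describes strapping in and a link that "permits abducting the legs while seated to facilitate donning and doffing the device". It also states: "There is no comparator device in this single -arm study".

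Section 22 lists falling, blood pressure instability or arrhythmia tied to standing or activity, and fractures tied to taking part in a therapy program. It mentions transfer out of the device only for a malfunction.

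**The concern.** The objective asks whether the regimen harms patients. The endpoint asks whether the device does. The two questions largely overlap but are not the same, and the protocol's own risk list includes hazards that it attributes to standing, activity or therapy and not to the device.

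Participants are inpatients, and under Section 12 prolonging an existing hospitalization makes an event serious, so an event in a session could readily qualify as an SAE. If the investigator judges that exertion, and not the exoskeleton, was the cause, Section 12 offers only one place to record that view: unrelated. The primary result is a small count, and the difference between zero and one matters to the safety statement made from it. A causality judgement that was never collected cannot be reliably recovered at the analysis stage, so this is not a detail that an analysis plan could settle later.

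**Working it through.** The protocol gives no figure to reproduce on this point: it has no expected SAE rate, no margin, and no derivation of the 40 Participants. The check is a comparison of texts, followed by an illustration of scale.

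**Step 1. How Section 12 would treat different SAEs**

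| SAE (assumed example) | Device grade that Section 12 allows | In the primary count? |
|---|---|---|
| Injury from device malfunction, including transfer out of it | Possibly or higher | Yes |
| Fall while walking in the EksoGT | Link in time and physiology, contribution possible | Very likely |
| Arrhythmia or blood pressure instability while standing or walking in the EksoGT, attributed to exertion alone | Possibly or unrelated, depending on the investigator | Undetermined |
| Fall in a session before donning or after doffing | Fits the related grades least well; unrelated is open | May be left out |
| Event of the underlying illness soon after a session | May be graded possibly | May be counted |

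Rows 3 and 4 are harms of the regimen that the endpoint can miss. Row 5 is an error in the other direction, and there is no comparator arm against which to see it.

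**Step 2. Whether other provisions supply the missing judgement**

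- Section 11 records, per session, "Any adverse events/complications noted following prior to training session and during present session". This gives occurrence and timing, not cause.
- Section 12 sends all SAEs to the Sponsor within 24 hours and has the DSMB adjudicate all of them. The only causality criteria stated are the device grades.
- Section 17 reports the number of adverse events without restricting it by cause. It specifies no breakdown by relation to training.
- Section 19 has case report forms reviewed for evidence of Participant risk.
- Section 23 has sites report research injuries to the Sponsor. That implies some view on whether the research caused the injury, but no grade.

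The event is therefore kept in every case. No provision requires a graded judgement on the session.

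**Step 3. Scale (illustration only; the event counts are assumptions)**

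Inputs: 40 Participants and at most 5 sessions each (Study Outline). Rate = x/40. Exact Poisson 95% limits: lower = χ²(0.025; 2x)/(2 × 40), upper = χ²(0.975; 2x + 2)/(2 × 40).

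| Assumed situation | x | SAEs per Participant | 95% limits |
|---|---|---|---|
| One regimen-caused SAE, coded unrelated | 0 | 0/40 = 0 | 0 to 0.092 |
| The same SAE, counted | 1 | 1/40 = 0.025 | 0.0006 to 0.139 |
| Counted, plus one underlying-illness SAE graded possibly | 2 | 2/40 = 0.050 | 0.006 to 0.181 |

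One reclassified SAE shifts the result by 0.025 per Participant in either direction. If all 40 × 5 = 200 possible sessions took place, the shift is 1/200 = 0.5 per 100 sessions. With at most one event per Participant, exact binomial limits agree in scale: 0/40 gives 0 to 8.8%, 1/40 gives 0.1 to 13.2%, and 2/40 gives 0.6 to 16.9%. The intervals overlap heavily and the protocol plans none, so they do not show how large the problem is.

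**The case against.** The strongest reply is that in this study the regimen is device use. Standing, walking and the blood pressure check before walking all take place in the EksoGT, and strapping in and out uses the device's own parts. Exertion in a powered exoskeleton fits the contribution wording of the lowest related grade. This largely stands: most SAEs that occur in the device would be counted. It does not bind an investigator who sees exertion as the sole cause, and it does not reach a fall before donning or after doffing.

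Second, an independent board adjudicates every SAE, so an investigator's coding need not be final. The adverse event forms are not shown, and the Section 12 list may not be exhaustive. That also stands as a limit on certainty. But the stated criteria concern only the device, and nothing in the protocol requires the board or the forms to judge the session.

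Third, device-related SAEs are a defensible endpoint for a cleared device in a new indication, and a wider count may take in more underlying-illness events. Both points are fair, and they are the reason to keep device-related SAEs as a separate line. They do not make the device count an answer to an objective written for the regimen.

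A reader might infer that regimen harms go unrecorded. The documents do not support that: Sections 11, 12, 17 and 23 keep and report them. A reader might also infer that transfers are a recognised hazard left outside the endpoint. Section 22 names transfer only after a malfunction, where the link to the device is plain. Nor does the phrase about a specific device show a fault in itself; with one device it can only mean the EksoGT.

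**Conclusion.** The mismatch is in the text and should be corrected, but its reach is narrow. The primary count does not fully answer the stated objective, because an SAE attributed to exertion or standing itself, or to a fall in a session outside the device, can be coded unrelated within the rules. Omission is possible, not certain.

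The size is unknown. The shift of 0.025 per Participant is simple arithmetic on an assumed event and is not evidence of how often this would occur. A reader might infer that the plan is built to understate harm; the text does not support that, since the count can also err upward through underlying-illness events graded as possibly related.

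The conclusion assumes that the forms and the adjudication follow the causality items stated in Section 12. If either already records relation to the session, the data-collection gap closes and only the endpoint definition needs attention.

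**What to change.** - **Section 12:** replace the single related-or-unrelated statement with two items, each graded unrelated, possibly, probably or definitely. The first is relation to the EksoGT, with the existing definitions. The second is relation to the study training session, with the same definitions and the session named in place of the device. Define the session as entry, donning, standing, walking, rest, doffing and exit, and exclude ordinary-care walking.
- **Section 4 and Study Outline:** define the primary endpoint as the number of SAEs at least possibly related to the EksoGT or to the study training session, per Participant and overall. Show device-related SAEs as a separate line, so that the present endpoint stays visible, and all-cause SAEs beside them.
- **Section 21, Sponsor responsibility (g):** extend it to adverse events related to the device or the training session.

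The cost is one more form item and wording changes that redefine the primary endpoint, so a protocol amendment with IRB approval is needed. The reported count may rise and may include some underlying-illness events graded as possibly related; the separate lines let a reader see this. The DSMB already adjudicates every SAE, so no new process is required.
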